#### $n_{new}=Max(n,n*).$

Therefore, if an increase in sample size is warranted by the re-calculation of the sample size requirements at the interim time point, it will only be reported how many more subjects are required in order to meet the study endpoint at

assumed a 2-sided alpha of 0.025 and power of 0.95. Note that, in accordance with the primary hypothesis, the sample size has been re-calculated under a 2-sided alpha=0.049 (instead of 2-sided alpha = 0.025) and a power of 0.90. This results in a sample size of 93 per group, or 117 when including 20% attrition and 124 when including 25% attrition. Thus the original sample size of 246 is sufficient for testing the primary endpoint with 90% power, and accommodate almost 25% attrition.

sufficient power. The sample size will not be reduced as a result of the sample size re-calculation. The sample size will only be increased, if the reassessment is so indicated. If the reassessment does not indicate an increase in sample size, then the study will continue as originally planned.

# 6.3 Missing Data and Sensitivity Analyses

# 6.3.1 Imputation of Missing Data in the Primary Analysis

The primary analysis will be performed on the ITT population. In the primary analysis, missing WOMAC Pain scores for subjects who are withdrawn due to reasons related to the index knee OA ("non-responders") will be considered Missing Not At Random (MNAR), and the subjects' baseline score will be carried forward in the analysis of WOMAC Pain. Scores missing for all other reasons will be considered Missing At Random and will be imputed using a Multiple Imputation method, which will replace each missing value with a set of plausible values that represent the variability around the choice of which value to impute. The monotone regression method will be used [22], and will include variables from **Table 1** (i.e. gender, age, BMI, race, and preop WOMAC Pain) as well as treatment group. As suggested in Bodner and White et al [23, 24], the number of imputations will reflect the percentage of incomplete cases. Approximately 15% attrition is estimated in the sample size calculation and thus approximately fifteen imputed datasets will be incorporated, and a seed of 20190516 will be used in generating the random numbers.

No imputation of missing values is planned for secondary or exploratory outcome variables.

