### 1.3 Randomization

Subjects will be randomized to either the APS or HA treatment group on a 1:1 basis. The subjects and investigators will both remain blinded throughout Phase I of the study. Assignment to treatment groups will be stratified by site and will use random block sizes. Specifically, designated unblinded personnel at each site will provide the masked syringe to the injecting health care provider. To protect the double-blind, the treating health care professional and evaluating health care professional will be different individuals. Assignment will not be revealed until after the blood has been drawn for nSTRIDE APS Kit processing.

The randomization plan will be produced using SAS v 9.4 or similar software. Balanced randomization with random block sizes (1:1, APS: HA) will be implemented. In the event that, post-randomization, no study treatment was given, randomization will not be reassigned; however, this case will not count toward the overall sample size. Randomization will continue with the next case enrolled until the minimum sample size is reached in both treatment groups. Randomization will be stratified by site, and each site will receive separate randomization plans using random predetermined block sizes that will remain undisclosed to the sites. The randomization file will be uploaded into the electronic data capture (EDC) system. Once the subject is enrolled into the EDC and has been identified as eligible for randomization, the randomization allocation will be visible within the EDC and viewable only by the unblinded research associate. The subject will be treated according to the contents of the displayed randomization allocation.

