#### Intent-to-Treat (ITT)

The ITT population includes all randomized subjects, regardless of whether they received an injection or not. This will be the population used for any data listings, for the primary study analysis, for safety analyses, and for demographic data summarized according to **Table 1**.

A table showing major and minor protocol deviations will be generated, comparing major and minor deviation frequency between the two treatment groups.

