# 7. Data Collection Time Points

Data will be collected at the screening visit, the injection visit, and at 1, 3, 6 and 12 months following the injection. After each subject completes all 12 month follow-up evaluations (Phase I), individual treatment allocation will be unblinded to the investigators. From this time-point on, only subjects will be blinded to study treatments resulting in a single-blind design during the longterm follow-up period (Phase II). During Phase II of the study, the subject may opt to get additional injections of their originally assigned treatment, or they may opt to crossover to the other treatment group and may receive multiple injections of the crossover treatment. Subjects may only crossover one time during the study. In Phase II, follow-up visits will occur at six month intervals until five years following the initial injection.

The follow-up visits will preferably be completed during an office visit to ensure subject compliance, but this is not mandatory and follow-up visits may consist of a structured telephone interview or electronic self-report with exception of annual visits at which radiograph is to be taken. The investigative center will contact the subject to complete the Follow-up and AE forms. The subject will be asked to complete a Patient Questionnaire.

A table showing the data collected at each time interval is presented in the study protocol.

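### Never-injected subjects stay in the primary ITT set and, if they have no 12-month score, are imputed with their assigned arm's full effect

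*SAP*

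**What the plan says.** SAP 1.3 (Randomization) foresees cases in which, after randomisation, "no study treatment was given, randomization will not be reassigned; however, this case will not count toward the overall sample size". Section 6 makes ITT the primary analysis and defines it so: "The ITT population includes all randomized subjects, regardless of whether they received an injection or not". Section 6.3.1 repeats the choice: "The primary analysis will be performed on the ITT population".

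Section 6.3.1 has two rules for a missing 12-month WOMAC Pain score. If the subject was withdrawn for reasons related to the index-knee OA, the "baseline score will be carried forward in the analysis of WOMAC Pain". Otherwise: "Scores missing for all other reasons will be considered Missing At Random and will be imputed using a Multiple Imputation method". The imputation covariates are gender, age, BMI, race, baseline WOMAC Pain and treatment group. None of them records whether the injection was given.

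Follow-up is timed from the injection. Section 7 states: "Data will be collected at the screening visit, the injection visit, and at 1, 3, 6 and 12 months following the injection". Table 2 in Section 3 likewise counts days since injection. Baseline pain is the screening score (SAP Table 1; Protocol synopsis, study design), so an uninjected subject has a baseline value. The Per Protocol definition draws on an mITT population that the SAP text does not define. No section gives never-injected subjects a rule of their own.

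**The concern.** For an uninjected subject, the score is missing for the same reason that there was no treatment, and the imputation model omits that reason. Conditioning on assigned arm alone amounts to assuming that an injection never given worked as well as one that was. An uninjected APS subject is filled in from APS subjects with observed scores, nearly all of them injected.

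The primary estimate would then be, in effect, the difference among injected subjects, reported as ITT. ITT is meant to carry the dilution that comes from subjects who do not receive their allocation, and here the imputation removes it. At stake are the size and label of the headline difference in WOMAC Pain.

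**Working it through.** **Inputs.** SAP 6.1, Table 15 gives a mean improvement of 7.20 (APS) and 4.93 (saline), pooled SD 4.06, and 123 planned per group. The SAP assumes that HA performs like saline. The shares never injected, fA (APS) and fH (HA), are not in the documents, so every share below is an assumption. Let u be the mean improvement among uninjected subjects, taken as equal in both arms.

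**The plan's own difference.** 7.20 − 4.93 = 2.27, as in Table 15.

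**What the planned rule targets.** If covariates are similar in injected and uninjected subjects, imputed means equal the arm means:

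(1 − fA) × 7.20 + fA × 7.20 − [(1 − fH) × 4.93 + fH × 4.93] = 2.27, whatever the shares.

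**What all randomised subjects would show.**

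ITT difference = (1 − fA) × 7.20 + fA × u − (1 − fH) × 4.93 − fH × u.

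Subtracting this from 2.27 and rearranging:

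overstatement = 2.27 × fA + (4.93 − u) × (fA − fH).

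With equal shares the second term vanishes and the ITT difference is 2.27 × (1 − f) for any u. With an HA-like outcome (u = 4.93) it also vanishes, and only the APS share matters. For fA above fH, a gap beyond 2.27 × fA needs an uninjected outcome below the HA mean as well as the unequal shares.

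| fA | fH | u | ITT difference | Overstatement |
|---|---|---|---|---|
| 1% | 1% | any | 2.25 | 0.02 |
| 3% | 3% | any | 2.20 | 0.07 |
| 5% | 5% | any | 2.16 | 0.11 |
| 10% | 10% | any | 2.04 | 0.23 |
| 5% | 1% | 4.93 | 2.16 | 0.11 |
| 10% | 2% | 4.93 | 2.04 | 0.23 |
| 5% | 1% | 0 | 1.96 | 0.31 |
| 10% | 2% | 0 | 1.65 | 0.62 |

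Example, row 7: 0.95 × 7.20 − 0.99 × 4.93 = 6.84 − 4.88 = 1.96.

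For scale, the standard error of the difference at 123 per arm is 4.06 × √(2/123) = 0.52.

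**Simulation of the imputation.** The model was a regression on treatment group, baseline pain, age, BMI and sex (race was left out), with 15 imputations. Each arm had 123 treated subjects plus the uninjected, and the true difference was 2.27. At nominal equal shares of 2%, 5% and 10%:

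- imputed difference among never-injected subjects: 2.22, 2.30, 2.30;
- overall estimate under the planned rule: 2.24, 2.30, 2.29;
- overall estimate with both arms' uninjected imputed at the HA level: 2.19, 2.19, 2.06.

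The gaps between the last two lines (0.05, 0.11, 0.23) match 2.27 × f. Uninjected subjects do receive the full arm effect.

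**Type I error.** Under a true null with 10% uninjected in each arm, the planned rule rejected in 4.4% of runs at a two-sided level of 0.049.

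**Planned sensitivity analyses (SAP 6.3.2).** Both complete-case analyses drop subjects without a 12-month score. The tipping-point analysis shifts imputed values in the treatment group as a whole.

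**The case against.** The best answer is the tipping-point analysis. Never-injected APS subjects are among the values it shifts. Lowering all imputed APS improvements by 2.27, or by 7.20, with HA untouched moves the estimate against APS at least as far as correcting the uninjected alone. A conclusion that survives such shifts survives every scenario in the table, and the SAP requires disagreement between analyses to be discussed. This stands as protection for the conclusion. It does not correct the primary estimate or show how much of a shift is due to non-injection, and the range of shifts is not stated.

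The rule also does not catch everyone. A subject withdrawn for index-knee OA gets baseline carried forward. A 12-month score obtained anyway, for example by the telephone or electronic route in SAP Section 7, would be used as observed. The protocol synopsis screen-fails subjects not injected within 32 days and lets them re-screen, although how this applies after randomisation is unclear. These routes narrow the group without emptying it.

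A reader might infer that the error systematically favours APS because only APS needs to be prepared, and might take 1.96 (2.27 is 16% higher) or 1.65 as the likely size. The documents do not support this. They give no non-injection rate and do not mention preparation failure. All subjects have the blood draw, and SAP 1.3 withholds assignment until after it, so a failed draw or an earlier withdrawal can fall in either arm. Failure of APS preparation after that point is possible, but the unequal shares are assumed. The two figures also assume no improvement without injection, which is not the assumption behind the HA-model fix.

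**Conclusion.** The concern holds as a bias in the size of the primary estimate. A randomised subject who is never injected, has no 12-month score and is not withdrawn for index-knee OA is credited with the assigned arm's full effect. With equal shares and no difference between arms among the uninjected, the overstatement is about 0.02 to 0.07 points at 1% to 3%, and 0.11 to 0.23 at 5% to 10%. The lower range is small beside a standard error of about 0.52. Larger values require more non-injection in APS together with uninjected outcomes below the HA mean.

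It would be tempting to read this as a false-positive risk. The one null case tested, equal shares of 10%, gives 4.4% and does not support that reading. The sizes rest on the Table 15 means, on HA behaving like saline, and on assumed shares.

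**What to change.** In SAP 6.3.1, take never-injected subjects out of the arm-specific missing-at-random rule. In both arms, impute them from the model fitted to HA subjects, so that no APS−HA difference is credited. This still assumes an HA-like outcome for people who received nothing, and the SAP should say so. Add baseline carried forward for these subjects as a sensitivity analysis, use any 12-month score actually obtained, and report the number never injected by arm and reason.

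Also reconcile three statements: Section 1.3 (untreated cases do not count toward the sample size), the ITT definition (they are in the primary set), and the Per Protocol definition, which relies on an undefined mITT population.

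The cost is SAP wording and a few lines of code, best settled before unblinding. The APS−HA difference becomes slightly less favourable. With the standard combining rules the HA-model imputation was conservative in the simulation, with 2.5% rejection under the null at 10% uninjected.

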inclusion/ exclusion criteria. Baseline imaging acquisition and review are not required to be repeated. The Core Imaging laboratory will then be requested to re-issue an X-Ray eligibility report with the new subject ID. During the treatment visit, all subjects will have a blood draw, from which the APS will be prepared for injection. After all available joint fluid is aspirated and, according to randomization group assignment, approximately 2.5 milliliters (ml) of APS or 6.0 ml of HA will be injected into the joint. Needle placement in the joint may be verified using ultrasound (if standard of care). To ensure the subject will be blinded to the treatment assignment, the syringe (regardless of the study arm) shall be taped with opaque medical tape. The tape will be used to wrap the entire length of the syringe including the needle hub. To protect the double-blind, the treating health care professional and evaluating health care professional will be different individuals. Any AEs associated with the blood draw and/or injection procedure will be recorded. All subjects will be instructed to refrain from exceeding the pre-injection level of activity for 14 days. Efficacy and safety will be assessed at 1, 3, 6, 12, 18, 24, 30, 36, 48, and 60 months post injection. Subjects will be asked to abstain³

³ During follow-up subjects will not be asked to abstain from low-doses of aspirin taken for cardioprotection. Long-term treatment with low doses of aspirin – usually max 100mg/day – only has an antiplatelet effect. Aspirin in low dose would not be enough to impact any pain sensations. Also, the low dose aspirin is supposed to be taken every day when taken for cardio-protection, so they should remain consistent on their regimen throughout the study. Aspirin taken prior to the follow-up visits will not be documented as a Protocol Deviation. Sites will document the low-dose of Aspirin in the patient medical file

from analgesic use for 48 hours prior to assessments. They will complete the WOMAC, EQ-5D, and NRS for pain.

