#### 6.1 Sample Size

Data used to estimate sample size are from Zimmer Biomet study APSS-33-00, a randomized study comparing APS to saline in human subjects. This calculation assumes that hyaluronic acid will perform similarly to saline. Estimates of expected difference and pooled standard deviation from this study are shown in **Table 15**.

Group	n	Mean Improvement in WOMAC	St. Dev.	Mean Diff.	Pooled St. Dev.	Sample Size Each	Combined Plus 20% Attrition
		Palli				Group	
APS	30	7.20	3.25				
Saline	15	4.93	4.73	2.27	4.06	93	246

Table 15- Results from APSS-33-00

The calculation results in 93 per group. Results are based on a two-tailed alpha of 0.049 and statistical power of 90%.

Planned enrollment was increased to 123 per group to protect against attrition of approximately 25% in either treatment group.

<sup>1 Under the original sample size calculations, the sample size of 196 randomized (98 per group) was adjusted to accommodate potential dropout rate of approximately 20%, resulting in a total sample size of 246. This sample size

A maximum of 30 sites will participate in the study. Enrollment will be stopped at any site reaching a limit of 30% of planned study enrollment.

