# 6.3.2 Sensitivity Analyses

Scores for subjects who are withdrawn due to reasons related to the index knee OA are considered Missing Not At Random. In all of the ITT analyses described below, these subjects will be considered "non-responders", and the subjects' baseline score will be used in the analysis of WOMAC Pain.

The primary study analysis assumes that the all other missing data is Missing At Random (MAR).

In order to investigate the assumption that the missing data (excluding the non-responders who are withdrawn for reasons related to the index knee OA)

<sup>2 If data are severely non-normal based on a graphical review, then the predictive mean matching method will be used instead of the monotone regression method.

is MAR, sensitivity analysis of the primary study endpoint will be performed under assumption of other missing data mechanisms, as follows:

- 1. A complete case analysis on the ITT population (Missing Completely at Random (MCAR))
- 2. A complete case analysis on the Per Protocol population (Missing Completely at Random (MCAR))
- 3. A tipping point analysis on the ITT population, performed under the assumption that the data is not MAR or MCAR by searching for a tipping point that reverses the study conclusion. This analysis will examine the possibility that the distribution of missing responses will have a different expected value than that of the corresponding distribution of the observed responses. Thus, the analysis will generate multiple imputed data sets with a specified sequence of shift parameters that adjust the imputed values for observations in the treatment group (Missing Not At Random (MNAR)).

In the event the conclusion from one or more of the sensitivity analyses disagrees with the conclusion from the primary analysis, the sources of differences between them will be investigated and subjected to explicit discussion and interpretation.

Prior results indicate that the efficacy of APS and the saline control differs over time, but this difference is small until some point after the 6 month postinjection time point. Therefore, although carrying data forward from an earlier time is commonly applied as a sensitivity analysis, in this case it is likely to produce misleading results if applied to primary endpoints and so is not planned.

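### The primary imputation model leaves out the 1-, 3- and 6-month WOMAC pain scores, and its 15% attrition figure is not in the sample size section

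*SAP*

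**What the plan says.** SAP section 6.3.1 splits missing 12-month WOMAC pain in the ITT analysis into two groups. For withdrawals related to index-knee OA, the "baseline score will be carried forward in the analysis of WOMAC Pain". All other missing scores are multiply imputed by monotone regression, with predictive mean matching as the fallback if the data are severely non-normal. The named predictors are the Table 1 variables and arm: "i.e. gender, age, BMI, race, and preop WOMAC Pain) as well as treatment group". Section 6.3.2 confirms the assumption: "The primary study analysis assumes that the all other missing data is Missing At Random (MAR").

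Post-baseline pain is available. SAP section 7 states: "Data will be collected at the screening visit, the injection visit, and at 1, 3, 6 and 12 months following the injection". The Protocol synopsis (Study Design and Procedures) says "Efficacy and safety will be assessed at 1, 3, 6, 12, 18, 24, 30, 36, 48, and 60 months post injection" and has subjects complete the WOMAC at these assessments. SAP Table 5 analyses WOMAC pain change at 1, 3 and 6 months.

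On the number of imputations, section 6.3.1 says it should reflect the percentage of incomplete cases, then: "Approximately 15% attrition is estimated in the sample size calculation and thus approximately fifteen imputed datasets will be incorporated". Section 6.1 instead sets enrolment "to protect against attrition of approximately 25% in either treatment group". Its footnote gives 93 per group, "or 117 when including 20% attrition and 124 when including 25% attrition", and Table 15 is headed with 20%.

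**The concern.** Missing at random is always conditional on what is in the imputation model. Here the condition is baseline characteristics and arm. For someone who leaves after month 6, the most informative observed data are the pain scores up to that visit, and the stated model does not use them. The imputed value is what a completer with the same baseline and arm would be expected to score.

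The index-knee OA rule catches some of these subjects, but only those whose withdrawal is coded that way. Subjects in pain who are lost to follow-up, withdraw consent or give another reason go into the imputation model. If such dropout is more common, or more strongly tied to pain, in one arm, the primary treatment difference is biased. The direction depends on which arm loses more of these subjects. The primary test also opens the fixed sequence, so every secondary claim rests on it.

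The 15% statement is a smaller matter. It contradicts the section it refers to, and it sets the number of imputations.

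**Working it through.** **Attrition.** Inflating n per group for dropout d gives n/(1 − d). I take the SAP's 93 and 98 per group as given.

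- SAP footnote: 93/0.80 = 116.25, so 117; 93/0.75 = 124. Both reproduce.
- SAP's earlier calculation: 98/0.80 = 122.5, so 123 per group and 246 in all. This reproduces.
- At 15%: 93/0.85 = 109.4, so 110 per group (220 in all); 98/0.85 = 115.3, so 116 (232). Neither gives 123 or 246.
- Implied by 123 per group: 1 − 93/123 = 24.4%; 1 − 98/123 = 20.3%.

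So 15% is neither stated in section 6.1 nor implied by its figures. By the rule in section 6.3.1, the number of imputations m would be about 20 to 25. Relative efficiency is 1/(1 + λ/m). With a fraction of missing information λ = 0.25 it is 0.984 at m = 15, 0.988 at m = 20 and 0.990 at m = 25, so little is lost.

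**Where bias would come from.** Let π be the proportion imputed in an arm, and δ the average excess of imputed over true improvement in those subjects. The bias in the APS minus HA difference is π(APS)·δ(APS) − π(HA)·δ(HA). It cancels when both quantities are alike in the two arms.

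**Simulation.** There were 27 scenarios of 1,000 trials each, with 20 imputations and Rubin's rules.

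- From the SAP: 123 per arm, a true 12-month difference of 2.27, SD 4.06 (Table 15). The arm difference up to month 6 was set at 0.2 to 0.5, in line with the remark in section 6.3.2 that it is small until after then.
- Assumed, not in the documents: the dropout percentages; a 6/12-month correlation of 0.3 to 0.65; a share of dropouts coded as index-knee OA of 0 to 75%; a baseline/change correlation of 0.3; 2% per arm never injected; other dropout after month 1, 3 or 6, logistic in last observed pain (slope 0.25 per point); demographics not predictive.
- OA-coded dropouts were set to zero change and left out of the imputation fit. The target keeps that rule and uses true scores for everyone else.

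Bias at correlation 0.65, planned model / model with follow-up scores (negative works against APS):

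| Dropout APS v HA | none OA-coded | 50% | 75% |
|---|---|---|---|
| 10% v 25% | −0.284 / −0.007 | −0.131 / +0.006 | −0.066 / +0.005 |
| 25% v 10% | +0.281 / +0.004 | +0.134 / −0.001 | +0.070 / +0.003 |
| 18% v 18% | 0.000 / −0.005 | −0.005 / −0.005 | −0.005 / −0.003 |

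At correlation 0.3 with 10% v 25%, the pairs are −0.101 / +0.001, −0.058 / −0.009 and −0.025 / +0.001. Monte Carlo error is 0.004 to 0.008. The standard error of the difference is 0.55 to 0.57, and adding the follow-up scores lowers it by 0 to 1.4%.

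Hand check: in the top-left cell the arms differ by 15 percentage points of imputed subjects, so δ is about 0.284/0.15 = 1.9 points. With half OA-coded, 0.075 × 1.9 = 0.14 (simulated 0.131). With three quarters, 0.0375 × 1.9 = 0.07 (simulated 0.066). A separately coded simulation of the top row gave −0.29, −0.15 and −0.08, and within 0.01 of zero once follow-up pain was added.

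**A harsher case.** Suppose 20% are missing in relation to 6-month pain, with a 6/12-month correlation of 0.5 to 0.7, imputation from arm alone and no baseline-carried-forward rule (all assumed). If the dependence on pain is equal in both arms, the estimate is 2.22 to 2.24 against a true 2.27. If it differs by arm, the estimate runs from 1.73 to 2.80. With 6-month pain in the model it is 2.26 to 2.30. This overstates the exposure under the actual plan, which has baseline pain in the model and the OA rule.

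**The case against.** **The list may not be closed.** The SAP says the model will include these variables, and the abbreviation before the list may only spell out what Table 1 contains. That reading is possible. But no section adds a post-baseline score, and a primary imputation model should be settled in advance, so the text needs changing on either reading.

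**The unequal dropout is imposed.** A 0.5-point early difference with slope 0.25 gives a dropout odds ratio of exp(0.125) = 1.13, for example 18% v about 20%. The 10% v 25% split is an odds ratio of 3.0. Nothing in the documents predicts it, and the case closest to section 6.3.2 shows almost no bias. This stands. The figures show what could happen, not what is expected.

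**The effect is modest.** With 50 to 75% of dropouts OA-coded, bias is 0.02 to 0.13, at most 6% of 2.27 and under a quarter of a standard error. When HA loses more subjects, it works against the superiority claim. This also stands.

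**The tipping-point analysis covers the harmful direction.** A bias of +0.28 corresponds to a shift of 0.28/0.25 = 1.1 points in the 25% of APS subjects who are missing, which a search would be expected to reach. This stands in part. The analysis probes departures from missing at random but does not repair the base it starts from. As written it shifts values in the treatment group, on the natural reading APS, so mis-imputed HA values stay as they are. The complete-case analyses do not use the follow-up scores of dropouts either.

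**Section 6.3.2 rejects use of earlier data.** It rejects carrying earlier scores forward because the arms are expected to separate after month 6. A regression with treatment in it estimates how earlier scores relate to month 12 and does not assume they stay unchanged. The objection does not reach this use.

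**Conclusion.** Both parts hold. The stated primary imputation model conditions on baseline and arm only and leaves out observed pain that is collected and analysed elsewhere in the plan. The resulting bias is conditional. It is within 0.01 of zero if pain-related dropout is alike in the two arms, and up to about 0.28 points (half a standard error, 12% of the planned 2.27) in either direction in the most unequal scenario tabulated. These sizes rest on assumed dropout rates, correlations and coding shares. The omission itself rests on the text alone. This should be corrected because it can be avoided with data already in hand, not because it threatens the trial. The 15% figure is an editorial contradiction with little numerical effect.

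**What to change.** In section 6.3.1, add WOMAC pain at 1, 3 and 6 months to the imputation model, in visit order, alongside the Table 1 variables and treatment. Monotone regression takes visits in sequence; specify an MCMC or fully conditional step for intermittent gaps. Keep the existing rule for index-knee OA withdrawals. Use the same model as the base for the tipping-point analysis in section 6.3.2.

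Replace the 15% statement with the figures in section 6.1, and set the number of imputations by the SAP's own rule: about 20 to 25, or the observed percentage of incomplete cases.

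The cost is SAP wording and a few lines of code. No new data are needed, and in the simulations precision did not suffer.
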